17.2. LABORATORY EVALUATIONS

Section 8.5.10 of the protocol identifies the hematology, chemistry, and urinalysis analytes collected for the study. Laboratory evaluations will be performed by local laboratories. Summaries and listings of laboratory data will be presented in international system (SI) of units, where applicable. Separate listings and summary tables (by study part and overall) will be produced for each laboratory test group (hematology, serum chemistries (liver, renal [with creatinine clearance, if creatinine is abnormal] and metabolism). Listings for coagulation profile and urinalysis will be provided.

Laboratory values that are reported as ‘below the detectable limit’ of an assay will be analyzed as half the detectable limit when required for analysis purposes but listed as originally reported. The following summaries will be provided for laboratory data:

- Post-baseline CTCAE grade 3 or 4 laboratory values in subjects who had normal limits at baseline
- Shift from baseline grade to worst post-baseline grade based on NCI CTCAE v4.03 (for analytes where CTCAE grading applies). A missing baseline grade will be assumed to be grade 0.
- Shift from baseline to worst post-baseline value that is $< 0.25 \times$ lower limit of normal (LLN) or $> 2.5 \times$ upper limit of normal (ULN) for analytes not gradable by NCI CTCAE v4.03.
- Post-baseline creatinine clearance meeting pre-defined criteria
- Post-baseline liver function test findings meeting potentially clinically significant abnormal criteria

The summaries will include the worst-case shift from baseline during the post-baseline period, which will include both planned (scheduled) and unscheduled visits after the first dose of study drug.

All laboratory data will be listed. Subjects with laboratory data outside of normal range will be flagged as “L” (Low) or “H” (High) in the data listing.

Additionally, listings of grade 3 or 4 (per NCI CTCAE) values and values $< 0.25 \times$ LLN or $> 2.5 \times$ ULN for analytes not gradable by NCI CTCAE will be provided. For subjects with a post-baseline analyte that is grade 3 or 4, all values for that analyte will be listed. Similarly, for subjects with a post-baseline analyte value that is $< 0.25 \times$ LLN or $> 2.5 \times$ ULN, all values for that analyte will be listed.

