Adverse events of special interest have been identified: CCI /T-ALL, MDS, AML, and other myeloid malignancies like MPN. As of 24 May 2019, there have been AESIs of myeloid malignancies reported in 5 of the 725 subjects in the adult lymphoma population treated with tazemetostat, including 2 cases of MDS (both possibly related), 2 cases of AML (both unrelated), and 1 case of MDS that later transformed to AML (possibly related). However, all 5 cases were heavily confounded by prior treatments. The degree of risk of myeloid malignancies remains uncertain based on paradoxical preclinical literature data, and the risk may be no greater than that expected in this subject population in general. There has been 1 AESI of CCI reported in a

pediatric subject. Refer to Section 10.4 of this protocol and to the current IB for further descriptions of AESIs.

As tazemetostat is a bromide salt, bromide levels were measured in a phase 1 study of tazemetostat in adults (Study E7438-G000-101) and in pediatric subjects (Study EZH-102). As of 24 May 2019, bromide elevation was reported in 3 (3.3%) of 90 pediatric subjects, all of which were considered to be related to tazemetostat treatment. See Section 1.6.2 for additional information. These elevated blood bromide levels were not associated with symptoms of bromide toxicity.

Treatment-emergent AEs are summarized in the Section 1.6.5 (anticipated safety profile) of this protocol and in the current IB.

Thus far, tazemetostat has shown clinical activity in subjects across the tazemetostat program, including objective responses and sustained disease stabilization in the indications shown below.

Table 1 Preliminary Efficacy Results for Tazemetostat Across Studies (ITT Populations)

Population Indication(s)	Study Number	N	ORR (%) (95% CI)	BOR of SD (%)
Adult population				
Synovial sarcoma (SS)	CCI	33	0	36.4
Malignant mesothelioma	EZH-203 (part 2)	61	3.3 (0.4-12.1)	62.3
Epithelioid sarcoma (ES)	CCI (Cohort 5)	62	15 (6.9-25.8)	56
Follicular lymphoma – mutant	E7438-G000-101 ph 2	45	73 (58.1-85.4)	22
Follicular lymphoma – wild type	E7438-G000-101 ph 2	54	33 (21.1-47.5)	30
DLBCL	E7438-G000-101 ph 2	234	16.2 (11.8-21.6)	20.5
Pediatric population				
ES (INI1-)	EZH-102	8	25 (3.2-65.1)	50
Various INI1-solid tumors combined (ATRT, MRT, other INI1-, ES, RTK, RMC, SS, chordoma, rhab, ME carcinoma)	EZH-102	85	13 (6.6-22.0)	20

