1.6.2 Hydrobromide Salt Formulation

An analysis of chloride levels in subjects on Study EZH-102 at the 1200 mg/m² dose level showed elevated chloride levels (beyond the ULN) in 5/7 subjects who had been treated at this dose level. Reviewing this finding further, subjects at lower dose levels (4/6 subjects at 900 mg/m², 4/6 subjects at 700mg/m² and 4/6 subjects at 520 mg/m²) also demonstrated elevated chloride levels.

Hyperchloremia is considered an artifact resulting from interference of serum bromide with the serum chloride assay (tazemetostat is a bromide salt). Artificially elevated serum chloride was also noted in repeat-dose nonclinical toxicology studies of tazemetostat in rats and monkeys at tazemetostat doses up to 1000 mg/kg/day. Ion exchange chromatography showed increased serum chloride in these nonclinical studies to be pseudo-hyperchloremia, representing increased bromide. Bromide levels were measured in the Phase 1 study of tazemetostat in adults. Bromide was within normal levels (<6.2 mmol/L) for all subjects taking the oral tablet formulation in doses up to 1600 mg BID. However, mean tazemetostat AUC₍₀₋₂₄₎ in children at the 1200 mg/m² dose level exceeded that observed in the 1600 mg BID dose group in adults from Study E7438-G000-101. Therefore, the assessment of bromide levels was instituted in Amendment No. 5 for all active and new subjects. Refer to Section 8.5.10 and Table 11 for the schedule of bromide level assessments and to Section 6.5.2 for dose modifications due to bromide toxicity. The chloride assay is being collected locally at every visit as part of the electrolyte panel, which is included in the standard blood chemistry assessment (Table 11).

For more details, refer to the tazemetostat Investigator's Brochure, Version 10.0.

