8.5.10 Clinical Laboratory Assessments

All clinical laboratory assays will be performed at local laboratories according to the laboratory's normal procedures. Chloride levels will be analyzed at both local and central laboratories. Bromide will be collected and sent only to a central laboratory for analysis. Please see Laboratory Manual for details. Reference ranges will be supplied by the laboratory and used to assess the laboratory data for clinical significance and out of range pathological changes. Abnormal laboratory values which are unexpected or not explained by the subject's clinical condition should be repeated until confirmed, explained, or resolved. Laboratory value changes starting from the initial tazemetostat exposure will be recorded in the eCRF as an AE if clinically significant.

Hematology: Hemoglobin, hematocrit, WBC, differential blood count with ANC, and platelet count assessments are performed at Screening and at regular intervals during each treatment cycle. Also, a peripheral blood smear will be collected along with normal hematology testing at screening and on day 1 of each cycle and assessed for abnormal morphology and potential bone marrow aspirate/biopsy (see below).

Coagulation Profile: Partial thromboplastin (PT), partial thromboplastin time (PTT), and international normalized ratio (INR) are performed at Screening, as clinically indicated (for example, when an anticoagulant is started or when total bilirubin increases to 1.5 X ULN), and at Post-treatment/Early Termination.

Serum Chemistry: Serum chemistries will be performed at Screening and at regular intervals during each treatment cycle.

- Chemistries (liver function) include: alkaline phosphatase, ALT, AST, and either conjugated (direct) bilirubin (where possible), or total bilirubin
- Chemistries (renal function) include: blood urea nitrogen, creatinine, electrolytes including sodium, potassium, chloride, and bicarbonate
- Chemistries (metabolism) include: albumin, calcium, magnesium, glucose, phosphorus, total protein, and triglycerides

Bromide Levels: Bromide levels will be measured pre-dose on Day 1 of Cycle 1; on Day 1 of every cycle thereafter; and at Post-Treatment/Early Termination visit.

Urinalysis: Urinalysis testing to include at minimum: glucose, blood, protein, and pH will be performed at Screening, on Cycle 1, Day 1, and on Day 1 every cycle thereafter and at Post-Treatment/Early Termination visit.

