14.5.4 Clinical Laboratory Evaluation

All clinical laboratory parameters will be standardized according to the International System of Units (SI) prior to summarization. Separate listings and summary tables (by cohort and overall) will be produced for each laboratory test group (complete blood counts, serum chemistries (liver, renal [with creatinine clearance, if creatinine is abnormal] and metabolism), coagulation profile, and urinalysis).

Low, normal, and high (LNH) classifications will be applied to determine whether the laboratory test value was below (L), within (N), or above (H) its reference range. Shifts from baseline in LNH classification and CTCAE grades for each parameter will be summarized by cohort and overall. The summary will include the worst-case shift from baseline during the post-baseline period, which will include both planned (scheduled) and unscheduled visits after the first dose of study drug. Subjects with laboratory data outside the normal range will be flagged as “L” (Low) or “H” (High) in the data listing.

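### The SAP's laboratory summary tables, though not its listings, are poorly suited to the known bromide and chloride signal: no bromide summary is named, and analytes without a CTCAE grade are tabulated only beyond 2.5 × ULN

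*SAP*

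**What the plan says.** **Collection.** Protocol 8.5.10 sets the schedule: "Bromide levels will be measured pre-dose on Day 1 of Cycle 1; on Day 1 of every cycle thereafter", with a further sample at the end-of-treatment visit. It also fixes the source: "Bromide will be collected and sent only to a central laboratory for analysis". Chloride is analyzed both locally and centrally.

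**Protocol analysis.** Section 14.5.4 plans: "Shifts from baseline in LNH classification and CTCAE grades for each parameter will be summarized by cohort and overall". The test groups named there are blood counts, chemistries, coagulation and urinalysis. Bromide is not named, and 8.5.10 lists it apart from the chemistries.

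**SAP analysis.** Section 3.2 openly replaces the low/normal/high shifts with shifts to the worst post-baseline CTCAE grade, to give a more focused display. Section 17.2 adds a rule for ungraded analytes: shifts to a worst value below 0.25 × LLN or above 2.5 times the "upper limit of normal (ULN) for analytes not gradable by NCI CTCAE v4.03". On source it says: "Laboratory evaluations will be performed by local laboratories". Its summary tables cover hematology and the liver, renal and metabolism chemistries. Bromide appears in the SAP only in the account of the dose decision (section 3.1).

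**Listings.** SAP 17.2 also says: "All laboratory data will be listed. Subjects with laboratory data outside of normal range will be flagged as" low or high.

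**The concern.** Bromide is the laboratory signal that helped shape this trial. Protocol 1.5.2.2 records that the Rolling 6 rules supported going on to 1600 mg/m². The safety committee instead took 1200 mg/m² BID into expansion, citing elevated bromide together with pharmacodynamic data, on the understanding that bromide would be watched closely. Bromide has its own dose-modification table (Table 8), is singled out in the rules for suspending expansion (3.4.2) and is a named potential risk (1.6.5).

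A clinical study report built from SAP 17.2 should therefore say how many children reached which bromide level, at which starting dose. As written, either bromide falls outside the tables altogether, because it is a central assay in none of the named groups, or it falls under a cut-off that may lie above the protocol's own top band. Chloride, which Protocol 1.6.2 treats as a marker of bromide interference, may meet the same cut-off. What is at stake is the tabulated incidence on which the safety summary would draw.

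**Working it through.** **1. The documents' own figure.** Protocol 1.4.2 states that "bromide elevation was reported in 3 (3.3%) of 90 pediatric subjects". 3/90 = 3.3%, which reproduces. It counts reported elevations; the number of those 90 with a bromide result is not given.

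**2. Bromide cut-off at the only stated limit.** Protocol 1.6.2 says of the adult study: "Bromide was within normal levels (<6.2 mmol/L"). Conversion uses 79.904 g/mol, a physical constant not in the documents.

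- ULN: 6.2 × 79.904 / 10 = 49.5 mg/dL
- SAP cut-off: 2.5 × 6.2 = 15.5 mmol/L; 15.5 × 79.904 / 10 = 123.9 mg/dL
- Start of Table 8's top band: 75 × 10 / 79.904 = 9.39 mmol/L; 9.39 / 6.2 = 1.51 × ULN

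At this limit, values above 75 and up to 124 mg/dL lie in the protocol's highest band but below the SAP's summary threshold.

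**3. Range over the unknown pediatric ULN.** The central laboratory's pediatric limit is not in the documents, so the ULNs below are assumptions.

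| Assumed ULN (mmol/L) | 2.5 × ULN (mmol/L) | mg/dL |
|---|---|---|
| 1 | 2.5 | 20.0 |
| 2 | 5.0 | 40.0 |
| 3 | 7.5 | 59.9 |
| 3.75 | 9.375 | 74.9 |
| 5 | 12.5 | 99.9 |
| 6.2 | 15.5 | 123.9 |

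The crossing point is 75 / 2.5 = 30 mg/dL, and 30 × 10 / 79.904 = 3.75 mmol/L. Above that ULN the cut-off exceeds the start of the top band; below it, it does not.

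**4. Chloride.** Protocol 1.6.2 gives 5/7 subjects beyond the ULN at 1200 mg/m² and 4/6 at each of 900, 700 and 520 mg/m².

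- Sum: (5 + 4 + 4 + 4) / (7 + 6 + 6 + 6) = 17/25 = 68% (exact 95% CI 46% to 85%)
- With the 3/6 evaluable subjects that Protocol 1.5.2.2 gives at 1200 mg/m²: (3 + 12) / (6 + 18) = 15/24 = 62.5%

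Baseline values are not given, so these are upper bounds for normal-to-high shifts. The elevations are described only as beyond the ULN. At an assumed chloride ULN of 100 to 115 mmol/L, the SAP cut-off would be 250 to 288 mmol/L. If chloride is ungraded, such elevations would be unlikely to enter the shift table, whereas a low/normal/high shift would count those that were normal at baseline.

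**5. Other routes.** Protocol 10.5 makes elevated bromide an event of clinical interest, reported through the SAE procedure whether or not serious, so reported cases can appear by preferred term in the TEAE tables. The SAP plans no table for events of clinical interest, and its special-interest table draws on Protocol 10.4, not 10.5. Protocol 10.2 keeps laboratory abnormalities that needed no intervention out of the AE data and sends them to the laboratory section of the report, which is what SAP 17.2 defines.

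**The case against.** The other side has real weight.

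- **Listings.** All laboratory data are to be listed with out-of-range flags. A reader might infer that the plan hides the signal or displays ungraded analytes only past the cut-off. The documents do not support that: the cut-off governs the summary table and one extra listing. It remains unstated whether centrally assayed bromide belongs to the full listing.
- **Event reporting and monitoring.** Reported bromide elevations enter the TEAE tables, and AE-driven dose reductions and interruptions are tabulated. Committee monitoring during expansion does not depend on SAP 17.2. This stands, but it gives counts of reported events, without a denominator of subjects tested.
- **Under-reporting.** A reader might set chloride at 17/25 against bromide at 3/90 and conclude that event reporting misses most cases. That does not follow. These are different analytes in different populations, and routine bromide testing began only with Amendment 5, for active and new subjects.
- **Declared change.** SAP 3.2 announces the move to CTCAE shifts with a reason, and Protocol 14.3.3 allows documented changes. Since 14.5.4 names no bromide group, a bromide shift table is an addition rather than a clear promise withdrawn.
- **Unknown inputs.** If the pediatric ULN is 3.75 mmol/L or lower, the gap above 75 mg/dL disappears. If chloride is gradable under CTCAE v4.03, the grade-shift table covers it. Neither can be settled from the documents.

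**Conclusion.** The point holds for the summary tables. No bromide summary is named, and the local-laboratory wording leaves it open whether bromide enters the tables at all. That does not depend on any assumed limit.

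The cut-off argument is conditional. For bromide, the threshold is 124 mg/dL at the one stated limit, against a top band starting above 75 mg/dL; over assumed ULNs of 1 to 6.2 mmol/L it ranges from 20 to 124 mg/dL. For chloride it rests on two assumptions: no CTCAE grade, and a ULN of 100 to 115 mmol/L. Neither the listings nor event reporting supplies a tabulated incidence among subjects with a result.

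It would go too far to say that the safety conclusion would be falsely reassuring, since the listings and event tables remain. This is a SAP revision that should be made; it does not touch the primary endpoint.

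**What to change.** In SAP 17.2:

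1. State that central bromide data are included in the laboratory tables and listings, and say which chloride source (local or central) feeds the tables.
2. Add a table of maximum post-baseline bromide using the existing Table 8 bands (10-50, >50-75 and >75 mg/dL) plus a category below 10 mg/dL, which Table 8 does not cover. Present it by starting dose and cohort, with subjects having at least one post-baseline bromide result as the denominator. The grouping matters because SAP 17.2 presents laboratory tables by study part, while Protocol 5.3 gives both 520 and 1200 mg/m² BID as starting doses for newly enrolled subjects.
3. Keep the low/normal/high shift table of Protocol 14.5.4 for chloride, and apply it to bromide, in place of the 2.5 × ULN rule.

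The cost is SAP wording and two extra tables from data already collected. The bands serve only as reporting categories; no clinical rule changes.

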17.3. ELECTROCARDIOGRAM EVALUATIONS

Single 12-Lead ECG measures will be collected according to the schedule of assessments in Appendix 3. Triplicates or additional unscheduled time points may be collected, if clinically indicated. When triplicates are collected, the averages (as calculated by the central ECG vendor ERT) will be used in the summaries.

The following pre-dose and post-dose 12-lead ECGs parameters will be collected at select scheduled time points:

- PR Interval (msec)
- RR Interval (msec)
- QRS Interval (msec)
- QT Interval (msec)
- QTc, Fridericia [QTcF] Interval (msec)
- HR (bpm)

The following summaries will be provided for the 12-lead ECG measurements listed above:

- Shift from baseline to worst post-baseline in QTcF status categorized as markedly abnormal or not (defined in the table below)
- Number and percentage of subjects whose worst-case changes from baseline in QTcF measurements meet markedly abnormal criteria (described in the **Table 5** below).

Table 5: QTcF Marked Abnormality Criteria

QTcF Measure	Markedly Abnormal Criteria
Observed Measures	450–480 msec, inclusive [CTCAE grade 1] 481–500 msec, inclusive [CTCAE grade 2] > 500 msec [CTCAE grade 3 or higher]
Observed Change from Baseline	31–60 msec, inclusive, increase from baseline >60 msec increase from baseline

The listings will include the individual ECG values and other information collected from the 12-lead ECG. QTcF measures meeting the markedly abnormal criteria as defined in the table above will be flagged on the listing.

17.4. VITAL SIGNS

Weight (kg) and height at screening (cm), as well as vital signs for systolic blood pressure (mmHg), sitting diastolic blood pressure (mmHg), sitting heart rate (bpm), respiratory rate (breaths/min), and temperature (C°) will be collected and listed. Summaries of heart rate, temperature, systolic blood pressure, and diastolic blood pressure will be based on markedly abnormal criteria defined in **Table 6** below:

Table 6: Vital Signs Marked Abnormality Criteria

Vital Sign	Markedly Abnormal Criteria
Heart rate (bpm)	< 60 bpm > 100 bpm
Temperature (°C)	≤ 35 °C ≥ 38 °C
Systolic blood pressure (mmHg)	120-139 mmHg, inclusive (CTCAE grade 1) 140–159 mm Hg, inclusive (CTCAE grade 2) ≥ 160 mmHg (CTCAE Grade 3)
Diastolic blood pressure (mmHg)	80–89 mmHg, inclusive (CTCAE grade 1) 90–99 mm Hg, inclusive (CTCAE grade 2) ≥ 100 mmHg (CTCAE grade 3)

Incidence of markedly abnormal worst-case values will be presented. For heart rate and temperature, both high and low values will be presented separately such that subjects can be counted in both categories. Markedly abnormal vital sign values will be flagged as such on the vital signs listing.

